6.9 SENSITIVITY ANALYSES

To evaluate of the robustness of the primary efficacy analysis, the binary endpoint based on the NRI in PP analysis set will use the same analysis methods for FAS as described in Section 6.2.1.

6.10 MULTIPLICITY

A closed hierarchical procedure will be used to control for multiple comparisons for the primary endpoint and the first secondary endpoint. The order of testing will be primary endpoint, followed by the secondary endpoint of clinical remission at Week 12. If the null hypothesis for the primary endpoint is not rejected, the testing procedure will be terminated. The subsequent analysis of clinical remission would be considered exploratory.

7 SAFETY ANALYSES

Safety will be evaluated via descriptive statistics and point estimates for patients in Safety Analysis Set. No inferential testing for statistical significance will be performed.

7.1 ADVERSE EVENTS

7.1.1 ADVERSE EVENT DICTIONARY

All AEs will be classified according to the Medical Dictionary for Regulatory Activities (MedDRA) dictionary. System organ class (SOC) and preferred term (PT) will be provided in the AE dataset.

7.1.2 ADVERSE EVENT SEVERITY

The severity of AEs will be graded according to the National Cancer Institute (NCI) Common Terminology Criteria for Adverse Events (CTCAE) version 5.0 (27 November 2017). The general categories for each grade are presented in Table 6.

Table 6 Adverse Event Severity Grading

Grade	Severity	Alternate Description
1	Mild	Asymptomatic or mild symptoms; clinical or diagnostic observations only; intervention not indicated
2	Moderate	Minimal; local or noninvasive intervention indicated; limiting age appropriate instrumental ADL
3	Severe	Severe or medically significant but not immediately life-threatening; hospitalization or prolongation of hospitalization indicated; disabling; limiting self-care ADL
4	Very severe, life-threatening, or disabling	Life-threatening consequences; urgent intervention indicated
5	Death related to AE	Death related to AE

7.1.3 RELATIONSHIP OF ADVERSE EVENT TO STUDY TREATMENT

The relationship of the AE to study treatment (PRA023) will be assessed by the investigator. The Investigator will define the relationship of an AE to the study drug by selecting one of the following categories:

- Related: There is a reasonable possibility that there is a causal relationship between the study drug and the AE.
- Not Related: There is not a reasonable possibility that there is a causal relationship between the study drug and the AE.

Relationship (causality) to study procedures should be determined for all pre-treatment-emergent events and AEs. The relationship should be assessed as Related if the Investigator considers that there is reasonable possibility that an event is due to a study procedure. Otherwise, the relationship should be assessed as Not Related.

7.1.4 SERIOUS ADVERSE EVENTS

Serious adverse events will be identified and captured as SAEs if AEs met the definitions of SAEs that were specified in the study protocol (Section 10.1.4).

7.1.5 ADVERSE EVENT OF SPECIAL INTEREST

An infusion reaction is defined as adverse events reported within the terms of hypersensitivity MedDRA SMQ (20000214) that occurred within 1 hour after the end of study drug infusion. A peri-infusion reaction is defined as adverse events reported within the terms of hypersensitivity SMQ (20000214) that occurred within 24 hours after the end of study drug infusion.

An infection is defined as those events coded under MedDRA body system of Infection and Infestation.

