## 5.4 PRA023 Administration

All doses of PRA023 will be administered intravenously as a 30-minute infusion using a calibrated infusion pump by the appropriately designated study staff at the investigational site.

Treatment of subjects with monoclonal antibodies may result in inappropriate immune responses and range from mild events with no apparent clinical manifestations to life-threatening or catastrophic reactions. Signs and symptoms of these events may develop during or shortly after infusion. As such, subjects must be closely monitored during administration of PRA023. Post-infusion observation period during the first 2 infusions (Week 0/Day 1 and Week 2) should be 1\* hour and subsequent infusions should be 30 minutes (Table 2 and Table 3).

Some of the major safety concerns associated with immunogenicity are anaphylaxis, cytokine release syndrome, “infusion reactions”, and non-acute reactions such as delayed hypersensitivity.

The information below is provided as guidance to assess anaphylaxis, but the clinical judgment of the Investigator should be considered as well.

Anaphylaxis is a serious, acute allergic reaction characterized by certain clinical features. Signs and symptoms of anaphylaxis may include:

- Generalized hives, pruritis/itching, flushing, swollen lips/tongue/uvula
- Symptoms of respiratory compromise (e.g., dyspnea, wheeze/bronchospasm, stridor, reduced peak expiratory flow, hypoxemia)
- Reduced blood pressure (systolic blood pressure of less than 90 mm Hg or greater than 30% decrease from baseline) or associated symptoms of end-organ dysfunction (e.g., hypotonia [collapse], syncope, incontinence)
- Persistent gastrointestinal symptoms (e.g., crampy abdominal pain, vomiting)

If a subject experiences anaphylaxis, PRA023 administration should be discontinued immediately and permanently. If a subject experiences symptoms that may be attributed to hypersensitivity reaction or delayed hypersensitivity (e.g., fever, rash, arthralgia, myalgia, hematuria, proteinuria, serositis, central nervous system complications, or hemolytic anemia), PRA023 infusion should be stopped.

In the event that symptoms are mild or minor in severity, at the discretion of the Investigator, the infusion may be restarted at a slower rate if symptoms are resolved within 1 hour after stopping the infusion. If symptoms return, PRA023 should be discontinued immediately and permanently.

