**Table 2 Schedule of Study Assessments – Induction Period**

Study Week	Study Visit							Early Termination	NOTES
	0	1	2	6	10	12			
	Study Day	1	8	15	43	71	85		
Visit window (days)	0	±1	±3	±3	±3	±3			
Procedure									
Eligibility Confirmation	X								
Randomization	X								Via IRT system
Complete Physical Examination						X	X		
Targeted Physical Examination	X		X	X	X				
Vital Signs	X	X	X	X	X	X	X		Heart rate, temperature, blood pressure; Take pre-dose (no more than 30 minutes pre-infusion), end of infusion, and end of observation period.
Weight	X	X	X	X	X	X	X		Needed for CDAI assessment
ECG	X					X	X		
Adverse Events Assessment	X	X	X	X	X	X	X		
Concomitant Medication	X	X	X	X	X	X	X		
Efficacy Assessments									
Ileocolonoscopy with Biopsy						X	X		Ileocolonoscopy to be performed within 10 days after Week 12 visit, or at early termination visit
Review eDiary Data from Subjects	X	X	X	X	X	X	X		Remind subjects to record in their eDiary daily
CDAI Assessment	X	X	X	X	X	X	X		
PDAI	X					X	X		
Fistula Drainage Assessment	X		X	X	X	X	X		
IBDQ	X			X		X	X		
Laboratory Testing									
CBC	X	X	X	X	X	X	X		
Chemistry Panel	X		X	X		X	X		
Fasting Lipid Panel	X					X	X		

	Study Visit							NOTES	
	Study Week	0	1	2	6	10	12		Early Termination
	Study Day	1	8	15	43	71	85		
Visit window (days)	0	±1	±3	±3	±3	±3			
Procedure									
Urinalysis	X		X	X		X	X		
Urine Pregnancy Test (WOCBP only)	X			X		X	X		
Pharmacokinetics	X a	X	X b	X b	X a	X	X	a. The PK sample at Week 0/Day 1 and Week 10 must be taken pre-dose, immediately following the end of infusion (within 30 minutes), and 1 hour after the end of infusion. b. The PK sample taken at Weeks 2 and 6 must be taken pre-dose (within 30 minutes prior to dosing).	
Immunogenicity	X a		X a	X a		X	X	a . To be taken pre-infusion	
Biomarkers									
Biomarkers	X		X	X	X	X	X	Serum at all visits; additional whole blood at Weeks 0, 6 and 12	
Soluble TL1A	X		X	X	X	X	X		
hsCRP	X	X	X	X	X	X	X		
Fecal Calprotectin	X			X		X	X		
Infusion	X		X	X	X			Include date, start and stop time, volume infused, and length of the IV infusion. Infusion observation period at Week 0/Day 1 and Week 2 will be 1 hour (2 hours for subjects in Czech Republic); 30 minutes for all subsequent infusions thereafter.	

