7.1.6 TREATMENT EMERGENT ADVERSE EVENTS

7.1.6.1 Definition of Treatment Emergent Adverse Events

Treatment Emergent Adverse Events (TEAE) are defined as following:

- AE onset date \geq 1st study treatment date; or
- AE worsened on or after the 1st study treatment date

AEs recorded prior to the first infusion of study treatment will be considered non-treatment-emergent. All reported AEs (treatment-emergent or not) will be listed. Only TEAEs will be summarized.

AEs of special interest including infections, acute infusion reaction (within 1 hour of completion of infusion), and peri-infusion reaction (within 24 hours of completion of infusion) will be summarized based on a pre-specified MedDRA list.

AEs occurring in subjects who are considered immunogenicity positive will also be summarized.

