7.1.7 SUMMARIES OF ADVERSE EVENTS

Treatment Emergent (TE) AEs will be summarized based on the Safety Analysis Set by treatment period and post-treatment period, separately.

Summary tables will be presented to provide the number and percentage of subjects experiencing any AEs, any severe AEs, any drug-related AEs, any SAEs, any drug-related SAEs, and any AEs leading to study drug interruption or discontinuation.

In addition to the above summary table, summary tables and listings of adverse events listed below will be provided.

- Summary of TEAEs by SOC and PT
- Summary of TEAEs by SOC, PT and Max Severity
- Summary of Severe (CTCAE Grade \geq 3) TEAEs by SOC and PT
- Summary of Related TEAEs by SOC and PT
- Summary of TESAEs by SOC and PT
- Summary of Related TESAEs by SOC and PT
- Summary of AEs in Follow-up by SOC and PT
- Listing of All AEs
- Listing of TESAEs or Death
- Listing of TEAEs Leading to Study Drug Interruption or Discontinuation

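### Read literally, SAP 7.1.5 leaves hypersensitivity events that start during an infusion out of both infusion-reaction summaries, and the looser wording elsewhere does not clearly bring them back.

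*SAP*

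**What the plan says.** SAP 7.1.5 gives the only operational definition, meaning a term list plus a time window. Events in the MedDRA hypersensitivity SMQ are infusion reactions if they are events "that occurred within 1 hour after the end of study drug infusion", and peri-infusion reactions if they are events "that occurred within 24 hours after the end of study drug infusion".

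SAP 7.1.6.1 then lists the same adverse events of special interest (AESI) in different words: "acute infusion reaction (within 1 hour of completion of infusion"), with a matching phrase for 24 hours. Protocol 8.3 and 9.2.7.1 use that looser phrase too. None of the four places mentions events during the infusion.

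Protocol 5.4 describes immune reactions to monoclonal antibodies and states: "Signs and symptoms of these events may develop during or shortly after infusion". It requires close monitoring during administration. It has the infusion stopped for symptoms of hypersensitivity, and for mild symptoms it adds that "the infusion may be restarted at a slower rate if symptoms are resolved within 1 hour after stopping the infusion".

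**The concern.** The definition and the clinical description do not cover the same period. The protocol expects reactions both during and after the infusion, while the SAP's windows cover only the time after it. A reaction that causes an infusion to be stopped necessarily begins before that infusion ends, so a program that applies the SAP rule to onset time would not flag it.

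Protocol 1.6 names hypersensitivity and infusion site reactions among the theoretical risks. Safety is a primary objective, and SAP section 7 plans descriptive summaries without inferential testing. A reader who wants to know how often infusion reactions occurred will go to the AESI summary, and that count could be too low.

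**Working it through.** The plan states no figure to reproduce. The check compares the windows and adds simple arithmetic on their length.

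**Inputs**
- Planned infusion length: 30 minutes (protocol 5.4: "All doses of PRA023 will be administered intravenously as a 30-minute infusion").
- Acute window: 1 hour, opening at the end of infusion (SAP 7.1.5).
- Peri-infusion window: 24 hours, opening at the end of infusion (SAP 7.1.5).
- Induction infusions: 4 (Weeks 0, 2, 6 and 10).
- Timing data: the schedule of assessments asks sites to "Include date, start and stop time, volume infused, and length of the IV infusion".

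**Which events each wording counts**, classifying by onset and taking the final stop time as the end of infusion:

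| Onset of event | SAP 7.1.5, 1 hour | SAP 7.1.5, 24 hours | Windows opened at start of infusion |
|---|---|---|---|
| During an infusion that is completed | out | out | in both |
| During an infusion that is stopped and not restarted | out | out | in both |
| During an infusion that is stopped, restarted and completed | out | out | in both |
| Within 1 hour after the end | in | in | in both |
| More than 1 and up to 24 hours after the end | out | in | peri-infusion only |

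The 24-hour category does not recover what the 1-hour category misses, because both open at the same moment.

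**Length of the gap**, for an uninterrupted infusion:
- Acute period from start of infusion to 1 hour after its end: 30 + 60 = 90 minutes. Not covered: 30/90 = 33%.
- Peri-infusion period from start to 24 hours after the end: 0.5 + 24 = 24.5 hours. Not covered: 0.5/24.5 = about 2%.
- Over the four induction infusions: 4 × 30 = 120 minutes per subject.
- An interrupted or slowed infusion lengthens the gap.

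**Does the looser wording close the gap?** A window of 1 hour either side of completion would cover all of an uninterrupted 30-minute infusion. It has two faults:
- It can miss onset in a stopped and restarted infusion. A pause of up to 1 hour followed by a slower restart can put onset more than 1 hour before completion.
- It reaches back before the infusion began: 60 − 30 = 30 minutes for the acute window, and 24 − 0.5 = 23.5 hours for the other. For doses after the first, it would admit events that precede that dose.

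The two-sided reading is therefore possible, but it is not a sound definition.

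**The case against.** Five points can be made on the other side.

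**Three of the four statements are not worded as strictly as SAP 7.1.5.** They can be read to include events during an uninterrupted infusion, and that may have been the intent. This stands as evidence of ambiguity. It does not rescue the definition, because SAP 7.1.5 is the one that would be programmed.

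**SAP 7.1.5 speaks of events that occurred, not of onset.** A reaction that began during the infusion and was still present after it ended could be counted on that reading. This stands in part. SAP 7.1.6.1 uses onset or worsening dates to define treatment emergence, so onset is the natural reading, but 7.1.5 does not say so. Even on the generous reading, a reaction that resolved before the end is excluded, including one that led to a stop, resolution and a completed restart.

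**The events are not lost to safety reporting.** This stands. A reader might infer that reactions during infusion go unreported, or that those interrupting an infusion are the most likely to disappear. The documents do not support either. All AEs are listed and TEAEs are tabulated. SAP 7.1.7 counts subjects with AEs leading to interruption or discontinuation and provides a "Listing of TEAEs Leading to Study Drug Interruption or Discontinuation". SAP 5.3.2 adds a by-subject listing of infusion interruptions. These are not AESI summaries, however, and a mild reaction that did not interrupt dosing would appear only in the general TEAE outputs.

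**One third is not an effect size.** This stands. A reader might infer that a third of infusion reactions would be missed. The documents give neither a reaction rate nor a distribution of onset times, so that inference has no basis.

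**Clock time of AE onset may not be collected.** The documents do not say whether it is, and SAP 7.1.6.2 handles incomplete dates by month and year. But the existing 1-hour window already needs onset time, so the change adds no new dependency on it.

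**Conclusion.** The point holds on the literal text of SAP 7.1.5: an event with onset during the infusion enters neither AESI category, contrary to what protocol 5.4 expects to see. The other three statements of the window are ambiguous and do not clearly include such events.

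The consequence is limited to an under-count, of unknown size, in the descriptive infusion and peri-infusion reaction summaries. The primary safety endpoint counts AEs, SAEs, AEs leading to discontinuation and markedly abnormal laboratory values, and is unaffected. So are the efficacy tests, the significance level and the sample size.

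This rests on two assumptions: that events are classified by onset, and that the end of infusion is the final stop time. The clock-time figures also assume an uninterrupted 30-minute infusion. The correction is worth making because the outcome is a named one and the change is small.

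**What to change.** In SAP 7.1.5, define:
- an acute infusion reaction as a hypersensitivity-SMQ event with onset from the start of infusion to 1 hour after its end;
- a peri-infusion reaction as a hypersensitivity-SMQ event with onset from the start of infusion to 24 hours after its end.

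State that the end is the final stop time when an infusion is stopped and restarted. Bring SAP 7.1.6.1 and protocol 8.3 and 9.2.7.1 into line, since changing 7.1.5 alone would leave the documents inconsistent. Confirm that the AE form records onset time on infusion days.

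The cost is a few words in each place and one extra condition in the AESI program, using start times that sites already record. SAP section 1 requires changes after finalization to be documented in the clinical study report with a rationale, which suffices if the SAP is not reissued. The protocol wording can wait for the next amendment. This is an analysis definition only and alters no dosing or infusion-management rule.

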7.1.6 TREATMENT EMERGENT ADVERSE EVENTS

7.1.6.1 Definition of Treatment Emergent Adverse Events

Treatment Emergent Adverse Events (TEAE) are defined as following:

- AE onset date \geq 1st study treatment date; or
- AE worsened on or after the 1st study treatment date

AEs recorded prior to the first infusion of study treatment will be considered non-treatment-emergent. All reported AEs (treatment-emergent or not) will be listed. Only TEAEs will be summarized.

AEs of special interest including infections, acute infusion reaction (within 1 hour of completion of infusion), and peri-infusion reaction (within 24 hours of completion of infusion) will be summarized based on a pre-specified MedDRA list.

AEs occurring in subjects who are considered immunogenicity positive will also be summarized.

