### 8.3 Evaluation of Safety Variables

Data will be summarized with respect to safety observations. Monitoring of AEs, physical examinations, vital signs, ECGs, safety and tolerability monitoring evaluations, clinical laboratory evaluations, and special procedures are detailed in [Section 6.3](#).

All available safety data for all randomized subjects who receive at least one dose of PRA023 will be included in the safety analysis, which will be primarily descriptive.

The safety variables will be:

- Hematology, chemistry, and urinalysis
- Vital signs
- ECG parameters
- Physical examination
- AEs and SAEs
  - AEs of special interest: infections, acute infusion reaction (within 1 hour of completion of infusion), and peri-infusion reaction (within 24 hours of completion of infusion)
  - AEs in subjects who are ADA positive

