6.3 SECONDARY EFFICACY ENDPOINTS

6.3.1 DICHOTOMOUS OR BINARY ENDPOINTS

The definition of the dichotomous secondary efficacy endpoints (i.e., responders) are listed in Table 3 below.

Table 3 Definition of Secondary Binary Endpoints

Outcome	Measure	Definition	Analysis Timepoints
Clinical Remission	CDAI	Crohn's disease activity index [CDAI] < 150	Week 12
Endoscopic and clinical improvement	SES-CD and CDAI	Decrease in SES-CD ≥ 50% AND reduction in CDAI ≥ 100 points from Baseline, or CDAI < 150	Week 12
Biomarker and Clinical Composite Improvement	hsCRP and CDAI	Decrease in hsCRP or fecal calprotectin ≥ 50% from Baseline and reduction in	Week 12

		CDAI \geq 100 points from Baseline, or CDAI < 150	
Clinical Response	CDAI	Reduction in CDAI \geq 100 points from Baseline or CDAI < 150	Week 12
PRO-2 remission	Abdominal pain score and Stool frequency	Average daily abdominal pain score \leq 1 point and average daily stool frequency \leq 3 points with abdominal pain and stool frequency no worse than Baseline	Week 12
Normalization of hsCRP	hsCRP	hsCRP < ULN, among subjects whose baseline hsCRP \geq ULN	Baseline, Week 12
Normalization of fecal calprotectin	fecal calprotectin	fecal calprotectin < ULN, among subjects whose baseline fecal calprotectin \geq ULN	Week 12
Anti-drug antibody (ADA) and Neutralizing antibody (Nab)	ADA and Nab	Positive ADA at any time; Positive Nab at any time	Over time

Abbreviations: SES-CD, Simple endoscopy score for Crohn's disease; CDAI, Crohn's disease activity index; hsCRP, High sensitivity C-reactive protein; PRO-2, Two component patient-reported outcome; ADA, Anti-drug antibody; Nab, Neutralizing antibody.

The proportion of clinical remission in FAS will be analyzed according to the method similar to the sensitivity analysis for the primary efficacy endpoint, in the case of missing data in CDAI at Week 12. If the resulting lower limit of 95% confidence interval is greater than 16%, the observed remission rate for the placebo treated patients from multiple prior CD trials ([1], [7], [8], [9], [10]), the null hypothesis for the first secondary endpoint of clinical remission at Week 12 will be rejected at a 1-sided significance level of 0.025.

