6.7 EVALUATION OF IMMUNOGENICITY

The proportion of subjects with any sample positive for ADA and the proportion of subjects with any sample positive for neutralizing antibody (Nab) will be summarized by the study period and dose using descriptive statistics. The PRA023 concentrations from all subjects and subjects with no sample positive for ADA will be summarized to assess whether ADA has an impact on PRA023 exposure.

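### AEs in antibody-positive subjects are summarised without regard to when the antibody appeared and with no antibody-negative group beside them

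*SAP*

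**What the plan says.** SAP 7.1.6.1 states: "AEs occurring in subjects who are considered immunogenicity positive will also be summarized". Protocol 9.2.7.1 has the same sentence, and protocol 8.3 lists among the safety variables "AEs in subjects who are ADA positive". None of these places says which subjects qualify as positive.

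The SAP's positivity rules stand elsewhere. Table 3 in SAP 6.3.1 has "Positive ADA at any time; Positive Nab at any time". SAP 6.7 uses "The proportion of subjects with any sample positive for ADA", and those proportions "will be summarized by the study period and dose using descriptive statistics". That period split applies to the ADA proportions, not to AEs.

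Two rules limit which events are shown and how they are divided in time. SAP 7.1.6.1 says "Only TEAEs will be summarized", which removes events before the first dose. SAP 7.1.7 says "Treatment Emergent (TE) AEs will be summarized based on the Safety Analysis Set by treatment period and post-treatment period, separately". The list of AE outputs in 7.1.7 contains no table by antibody status.

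An ADA-negative group does appear in two other analyses: as a subgroup for endoscopic improvement (SAP 6.2.2), and for PRA023 concentrations, where all subjects are shown along with those who never had a positive sample (SAP 6.7).

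**The concern.** Protocol 5.4 names anaphylaxis, cytokine release, infusion reactions and delayed hypersensitivity as major safety concerns tied to immunogenicity. A table of AEs in antibody-positive subjects will be read as information on that link.

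For that reading, order matters: a reaction before the antibody existed cannot have been caused by it. Under an ever-positive rule, a reaction at the first infusion in a subject who first tests positive at Week 12 is shown as an AE in an ADA-positive subject. The SAP times infusion reactions closely, as events "that occurred within 1 hour after the end of study drug infusion", but nothing relates that time to the antibody result.

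The percentage also needs something to be compared with. An AE rate in positive subjects alone does not show whether it is high or low for this population. The SAP provides the comparison for efficacy and for concentrations, but not for AEs.

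**Working it through.** The plan gives no figure for this point, so there is none to reproduce. The check has three parts.

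**1. Could any rule in the plan supply the order or the comparison?**

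| Rule | Place | Orders AEs around the antibody? | Gives an ADA-negative AE group? |
|---|---|---|---|
| AE summary in positive subjects | SAP 7.1.6.1, protocol 9.2.7.1 | No | No |
| Positive at any time | SAP Table 3 | No | No |
| Any positive sample | SAP 6.7 | No | No |
| Treatment-emergent events only | SAP 7.1.6.1 | Only around the first dose | No |
| Treatment and post-treatment periods | SAP 7.1.7 | No | No |
| ADA subgroup | SAP 6.2.2 | Not about AEs | Efficacy only |
| No positive sample | SAP 6.7 | Not about AEs | Concentrations only |

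**2. How much induction experience can be placed before the antibody?**

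Inputs from protocol Table 2 and SAP Appendix G: antibody samples at Week 0 (Day 1), Week 2 (Day 15) and Week 6 (Day 43), all pre-infusion, and at Week 12 (Day 85). Infusions are at Weeks 0, 2, 6 and 10. Assumption not in the documents: a constant AE rate over Days 1 to 85, so that share of time stands for share of events.

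The antibody arises at an unknown time between the last negative and the first positive sample. Only experience before the last negative sample clearly precedes detectable antibody:

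share = (day of last negative sample − 1) / (85 − 1)

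- First positive at Week 12, last negative at Week 6: (43 − 1)/84 = 42/84 = 50%. The Week 6 sample is taken before that day's infusion, so the Week 0 and Week 2 infusions precede it: 2 of 4.
- First positive at Week 6, last negative at Week 2: (15 − 1)/84 = 14/84 = 17%. Only the Week 0 infusion precedes it: 1 of 4.
- First positive at Week 2, last negative at Week 0: 0/84 = 0%, and 0 of 4.

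If the window is extended to the last follow-up sample, 84 days after a Week 10 dose (Day 71 + 84 = Day 155), the first two shares become 42/154 = 27% and 14/154 = 9%.

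**3. Would a crude positive-versus-negative comparison be enough?**

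A simulation with no true link between antibody and AEs was run under assumed values: 40–60% of subjects continue in the OLE to Week 50 and the rest are followed to Day 155; cumulative ADA is 10–30% by Day 85; there are 0.5–1 AEs per 84 days. The percentage with any AE came out about 3 to 9 points higher in ever-positive than in never-positive subjects. Longer follow-up brings both more samples and more AEs. These inputs are not in the documents, so only the direction and rough size are informative. A negative column is needed, but over mixed follow-up it does not replace the timing split.

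**The case against.** The strongest reply is that the plan is silent rather than wrong. The sentence fixes no layout, the safety section does not define positivity, and the ever-positive reading is carried over from Table 3 and 6.7. This is fair: a reader might infer that the SAP has decided against a comparison group or a timing rule, and the documents do not say so. What stands is that no other definition of positivity is available, so programming the sentence as written gives the ever-positive table.

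A second reply is that the information is not lost. A reader might infer that time order is irrecoverable, but the documents do not support that. SAP 7.1.7 plans a listing of all AEs, SAP 4.1 puts AE listings in chronological order within subject, and protocol section 9 promises individual data listings. With about 50 subjects, AE onset can be compared with sample dates by hand. Counts in negative subjects follow by subtraction from the all-subject tables if the layouts match. This lowers the importance of the point but does not supply a prespecified display.

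A third reply concerns size. A reader might take a first positive result at Week 12 to mean that all induction AEs and all 4 infusions preceded the antibody. That treats detection as onset, although the antibody may have arisen at any time after the Week 6 sample, and it ends the window on the sampling day. With follow-up to Day 155, the share before that first positive sample is (85 − 1)/154 = 55%. The last-negative figures above are the ones that can be defended.

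Finally, safety is descriptive with no testing (SAP section 7), and no sample size or efficacy test depends on this table. That stands in full.

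**Conclusion.** The point holds as a minor but concrete weakness in the safety analysis. As written, the summary mixes events from before and after the antibody was detected and has no ADA-negative group beside it, while the SAP provides such a group for efficacy and concentrations.

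For a subject first positive at Week 12, half of induction time and 2 of 4 infusions precede even the last negative sample. For one first positive at Week 6, the figures are 17% and 1 of 4. They rest on nominal sampling days, on the ever-positive rule being applied to the AE summary, and, where time is read as events, on a constant AE rate over induction. The documents give no expected ADA incidence, so the number of subjects affected cannot be stated.

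The effect is on how the immunogenicity safety table can be read, chiefly for infusion and hypersensitivity reactions.

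**What to change.** In SAP 7.1.6.1, define immunogenicity positive and separate subjects positive at baseline from those with treatment-emergent antibody. In 7.1.7, add a table of TEAEs and of infusion and peri-infusion reactions with ADA-positive and ADA-negative subjects side by side.

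For treatment-emergent positive subjects, split events by onset: before the first positive sample, or on or after it. Add a supportive version that cuts at the last negative sample, since samples are up to six weeks apart in induction (Day 43 to Day 85) and the true onset lies between the two. Neither cut is exact, which is why both are useful. Report baseline-positive subjects separately, because they have no earlier negative sample.

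The cost is SAP wording and one descriptive table from data already collected. The positive column will hold few events and will not support firm conclusions. If induction and OLE are pooled, the contrast will also reflect length of follow-up, and the table should say so.
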